11.1.2 Subjects enrolled under protocol rev AE and future revisions

[REDACTED]

11.2 Withdrawal

All subjects enrolled in the clinical study (including those withdrawn from the clinical study or lost to follow-up) shall be accounted for and documented. If a subject withdraws from the clinical investigation, the reason(s) shall be reported.

For US subjects: If such withdrawal is due to problems related to investigational device safety or performance, the investigator shall ask for the subject’s permission to follow his/her status/condition outside of the clinical study until the implanted investigational devices are approved by the FDA or the device is explanted.

Reasons for withdrawal include, but are not limited to:

- Subject who does not receive a Boston Scientific ImageReady MR Conditional Defibrillation System (no follow-up requirements)
- Subject who receive only a partial Boston Scientific ImageReady MR Conditional Defibrillation System (see section 11.3.4 for follow-up requirements)
- Subjects that have a PG or lead changeout that is not a Boston Scientific ImageReady MR Conditional Defibrillation System component (See Section 5)
- Subjects in Phase I who refuse to undergo the study require MR scan and are not willing to be rolled into Phase II
- Subjects already enrolled with previous protocol versions, who have not performed the MRI visit and who meet the updated exclusion criterion #5
- Subjects who fail the heart rhythm monitoring requirements at the MRI visit
- Physician discretion
- Subject choice to withdraw consent
- Lost to follow-up
- Death

While study withdrawal is discouraged, subjects may withdraw from the ENABLE MRI study and/or the VF Induction Sub-study at any time, with or without reason, and without prejudice to further treatment.

All applicable case report forms up to the point of subject withdrawal and a “Subject Status” form must be completed. Subjects who are “lost-to-follow-up” should have documented attempts to contact them prior to completion of the “Subject Status” form.

Additional study data may no longer be collected after the point at which a subject has been withdrawn from the study or withdraws his/her consent, for whatever reason. All open adverse events should be closed or documented as chronic. Data collected up to the point of subject withdrawal may be used.

11.3 Subject Status and Classification

Subjects enrolled in the ENABLE MRI study will be placed into one of six classifications, as defined below.

If a subject receives the PG or lead(s) listed in **Section 5** after enrollment, they will be treated as a de novo. De novo subjects are classified based on sections 11.3.1 to 11.3.5.

11.3.1 Intent

Intent refers to a subject who has been enrolled, but does not have the lead(s) or PG introduced into their body. There are no follow-up requirements for intent subjects. The

original informed consent form (ICF) and screening documentation for intent subjects should be maintained in the Center's files.

11.3.2 Consent ineligible

Consent ineligible refers to a subject who signed the ICF but meets exclusion criteria #3 or #5. As applicable, all adverse events need to be reported up to the point of withdrawal. There are no follow-up requirements for consent ineligible subjects. The original informed consent form (ICF) and screening documentation for consent ineligible subjects should be maintained in the Center's files. These subjects do not count towards the enrollment ceiling.

11.3.3 Attempt

Attempt refers to a subject who 1) has been enrolled in the Study, 2) has had anesthesia administered in preparation for the surgical implant procedure, 3) has had the lead(s) and/or PG introduced into the subject's body, but 4) is not successfully implanted with any portion of the ImageReady System during the implant procedure (meaning the subject is not successfully implanted with either the PG or lead(s)).

Attempt subjects must be followed 30 ± 7 days post-attempted ImageReady System implant to assure there are no associated adverse events, or to assure the resolution of any adverse events associated with the attempted ImageReady System implant.

11.3.4 Partial Implant

Partial Implant refers to a subject who is implanted with a component of the ImageReady System during the implant procedure, but does not end up with a complete ImageReady System. Due to the fact that these subjects do not have a full ImageReady System, according to the Conditions of Use in the *BSC MRI Technical Guide*, they shall not receive the MR Scan for the ENABLE MRI study.

- **For US subjects: If investigational leads were implanted, the subjects must be followed for safety.** These subjects must be followed at each time point required for the study until the implanted investigational leads are approved by the FDA or the device is explanted.
- **If there were no investigational leads implanted,** Partial Implant subjects must be followed 30 ± 7 days post- ImageReady System implant to assure there are no associated adverse events, or to assure the resolution of any adverse events associated with the ImageReady System implant, then withdrawn from the study.

11.3.5 Implant

Implant refers to a subject who is successfully implanted with the ImageReady System per the study protocol. These subjects are followed in accordance with the follow-up schedule and included in all analyses of safety and performance.

11.3.6 Existing Implant

Existing Implant refers to a subject who has a complete ImageReady System implanted prior to enrollment, per the study protocol. These subjects are followed in accordance with the follow-up schedule and included in all analyses of safety and performance.

11.4 Enrollment Controls

A total of 500 subjects at up to 70 investigational centers will be enrolled in this study.

[Redacted]

[Redacted]

[Redacted]

[Redacted]

[Redacted]

[Redacted]

[Redacted]

[Redacted]

[Redacted]

11.5 End-of-Study Action Plan

Boston Scientific Corporation reserves the right to terminate the study, or discontinue implanting at any stage but intends to exercise this right only for valid scientific or administrative reasons and reasons related to the protection of subjects. In the event of this occurrence, BSC will communicate to the investigators of the ENABLE MRI Clinical Study. The investigators will be responsible for communicating any information necessary to the subjects. BSC will support the physicians by providing recommendations for ensuring the safety of the subjects and the handling of any investigational components of the ImageReady System in the US until those components are approved by the FDA, which may include, but are not limited to:

- Standard of care procedures
- More frequent follow ups of the subject than per standard procedures
- Longer term follow up (beyond length of initial consent)
- Explanation of RELIANCE 4-FRONT or ACUIITY X4 leads upon careful risk-benefit analysis
- Other possible actions

If it becomes apparent that any of the investigational products will not be FDA-approved, a communication and study action plan for the subjects with those unapproved devices will be implemented.

12. Study Methods

12.1 Data Collection

A detailed list of procedures, testing and data collected required at the study visits are presented in Table 12-1. The table also has the study visits that are needed per study phase and per implanted device status.

- For Phase I subjects there will be a non-diagnostic study required MR scan (during the MRI visit)
- For Phase I subjects, the MRI and the MRI + 1 Month visits are required.
- For VF Induction Sub-Study subjects, VF Induction testing will be performed at the MRI + 1 Month Visit
- For "for cause" VF induction subjects, VF Induction testing will be performed ideally at the MRI + 1 Month Visit or up to 14 calendar days later
- For de novo implants (phase I), the Implant and Pre-discharge visits are required.

Table 12-1: Data Collection Schedule

Procedure / Assessment	Screening and Enrollment	Phase I: De novo implants only		Phase I only		Every Three-Month Visits***	Every Annual Visits*	Additional Visits	Medically necessary MRI
		Implant	Pre-Discharge	MRI Visit	MRI + 1 Month Visit				
Timeframe	De novo: ≤ 30 days prior to Implant Existing implant	Implant	3-72 hours from Implant	De novo: 6-9 weeks from Implant ^Δ Existing implant: within 6 weeks from Enrollment ^Δ	30 ± 7 days from MRI Visit	90 ± 30 days from MRI Visit	De novo: 365±90 days* from implant Existing implant: 365±90 days* from Enrollment	--	--
Informed consent form and process, including informed consent signature and date	X**	--	--	--	--	--	--	--	--
12 lead ECG & 10s rhythm strip	X (document exclusion #5)	--	--	X Pre MRI (HR monitoring)	--	--	--	--	X Pre MRI (HR monitoring)
Demographics	X	--	--	--	--	--	--	--	--
Physical assessment	X	--	--	--	--	--	--	--	--
Medical History, Comorbidities, Cardiac Disease History, Medications	X	--	--	--	--	--	--	--	--
ICD/CRT-D system implant	--	X	--	--	--	--	--	--	--
Device Evaluation (includes pace thresholds, intrinsic amplitudes, impedances, RV shock impedance)	--	X	X	X Pre & Post	X	X	X	O	O

Procedure / Assessment	Screening and Enrollment	Phase I: De novo implants only		Phase I only		Every Three-Month Visits***	Every Annual Visits*	Additional Visits	Medically necessary MRI
		Implant	Pre-Discharge	MRI Visit	MRI + 1 Month Visit				
Timeframe	De novo: ≤ 30 days prior to Implant Existing implant	Implant	3-72 hours from Implant	De novo: 6-9 weeks from Implant ^Δ Existing implant: within 6 weeks from Enrollment ^Δ	30 ± 7 days from MRI Visit	90 ± 30 days from MRI Visit	De novo: 365±90 days* from implant Existing implant: 365±90 days* from Enrollment	--	--
VF Induction Testing ("for-cause" or VF Sub-study)	--	--	--	--	X****	--	--	--	--
Beeper Assessment	--	--	--	X Pre & Post	--	--	--	--	X Pre & Post
Save All	--	--	--	X	X		X	O	O
Printout of device settings and history	--	X	X	X	X	X	X	X	X
MRI Conditions of Use	--	--	--	X	--	--	--	--	X
DICOM file from MR scanner	--	--	--	X	--	--	--	--	O
Adverse Events	X	X	X	X	X	X	X	X	X

Legend: X = Required; -- = Not required/ Not applicable; O = Optional; Δ Must be at least 6 weeks after any required surgical interventions to the ImageReady System;

* Annual visits will occur at 365 ± 90, 730 ± 90 and 1095 ± 90 days after implant (if de novo) or from enrollment (if existing implant) respectively.

** The informed consent process and subject signature of the informed consent form will occur before the implant procedure begins.

*** The first Every 3-month visit will occur 90 ± 30 days after MRI visit. Subsequent Every 3-month follow-up visits will be scheduled every three months (90 days ± 30 Days) from the previous scheduled study follow-up. If this visit is done, then the data is required.

**** The "for-cause" VF inductions may be performed up to 14 calendar days after the MRI + 1 Month Visit

12.2 Study Candidate Screening

Boston Scientific will collect information to document potential subjects who are considered as potential study candidates but are determined not to meet inclusion criteria prior to signing informed consent.

12.3 Informed Consent

All subjects who complete the informed consent process, sign and date the informed consent form will be evaluated for the following criteria:

- Radiologist approval to undergo MRI scan if metal objects in body (exclusion criterion #3)
- 12 lead ECG and 10s rhythm strip (either from the ECG machine or the BSC PRM) (exclusion criterion #5)

Source documentation for both of these exclusion criteria need to be retained in the patient medical file.

Subjects who meet these exclusion criteria will be considered Consent ineligible and will not count toward the enrollment ceiling.

Subjects who do not meet these exclusion criteria will be considered enrolled in the ENABLE MRI study and will count toward the enrollment ceiling.

In addition, subjects who meet none of the exclusion criteria for the VF Induction Sub-study and undergo the VF Induction Sub-Study informed consent process, sign, and date the ENABLE MRI VF Induction Sub-study informed consent form are considered enrolled in the Sub-study.

For Phase I de novo implants: Enrollment may occur up to 30 days prior to the implant procedure.

A summary of the data collected at enrollment is described in Table 12-1. The following assessments will be performed at Enrollment.

12.4 Screening and Enrollment Visit

The data to be collected at enrollment includes:

- Signed and dated informed consent to participate in the ENABLE MRI study
- Patient demographic data
- Physical assessment including height, weight and vital signs
- Medical history, comorbidities, cardiac disease history and medications.

Subjects who consent to participate in the VF Induction Sub-study will provide written informed consent.

A summary of the data collected at enrollment is described in Table 12-2.

Provide the subject with an EC/IRB approved ENABLE MRI Study identification card. The subject should be instructed to show the card at every hospitalization and ER visit.

12.4.1 Screening and Enrollment Source Data Requirements

Source data requirements at Screening and Enrollment are described in Table 12-2.

Table 12-2: Screening and Enrollment Source Documentation Requirements

Source Documentation Requirement	Disposition
Informed consent form and process, including informed consent signature and date.	Retain at center
12 leads ECG and 10s rhythm strip to document exclusion criterion #5	
Completed Radiologists Technical Source Form (applicable for subjects with metallic implants only)	
VF Induction Sub-Study informed consent and process, including informed consent signature and date, if applicable	
Demographics, including age, gender, race/ethnicity, etc.	
Physical assessment, including weight and height	
Medical History, Comorbidities, Cardiac Disease History, Medications	
Adverse Events	

12.5 Implant

For Phase I de novo subjects, the implant procedure will occur either on the same day as enrollment, after the subject signs and dates the informed consent form, or up to 30 days later.

The ImageReady System should be implanted and tested per standard procedures and in accordance with the Physician's Manuals for the associated PG and lead(s). To satisfy the MRI Conditions of Use (see Section 6), the PG must be implanted in the left or right pectoral (subcutaneous or sub-muscular) regions.

The implant procedure end time is defined as the time of device pocket closure. Record the end time in the electronic data capture (EDC) system.

Investigators will follow standard of care or standard center practices for the implant of the ICD/CRT-D system.

- For the VR ICD system, an ENDOTAK RELIANCE (DF4) or RELIANCE 4-FRONT RV⁸ lead must be successfully implanted unless the subject already has an existing functional ENDOTAK RELIANCE (DF4) or RELIANCE 4-FRONT RV lead.
- For the CRT-D system:
 - In the right atrium, a FINELINE II or INGEVITY⁹ RA lead or Port plug 7145 must be successfully implanted unless the subject already has an existing functional FINELINE II or INGEVITY⁹ MRI RA lead or Port plug 7145.
 - In the right ventricle, an ENDOTAK RELIANCE (DF4) or RELIANCE 4-FRONT RV⁸ lead must be successfully implanted unless the subject already has an existing functional ENDOTAK RELIANCE (DF4) or RELIANCE 4-FRONT RV lead
 - In the left ventricle, an ACUITY X4 LV lead must be successfully implanted unless the subject already has an existing functional ACUITY X4 LV lead.
- A DF-4 or IS-4 port plug cannot be used in place of the RV or LV lead.

A summary of the data collected at implant are described in Table 12-1.

12.5.1 Device Evaluation

All implanted leads will be evaluated through the implanted PG using the test parameters listed in Table 12-3:

- Manual pacing threshold tests, as defined in sections 12.5.1.1, 12.5.1.2 and 12.5.1.3.
- Sensing amplitude
- Impedance
- Shock impedance (RV lead only)

Record the measurements in the EDC system.

⁸ No de-novo RELIANCE 4-FRONT implants will occur in the US

⁹ INGEVITY is only available internationally outside of the US

Table 12-3: Test Parameters

Description	RA Threshold Test	RV Threshold Test	LV Threshold Test
Test Type	Amplitude	Amplitude	Amplitude
Pulse Width (ms)	0.5	0.5	0.5
Cycles per Step	3 (minimum)	3 (minimum)	3 (minimum)
Pacing Lead Configuration	Not Programmable	Not Programmable	Per HCP For MRI and MRI + 1 Month visits: The same LV Pacing Configuration must be used for threshold testing
Impedance Tests	RA Impedance Test	RV Impedance Test	LV Impedance Test
Pacing Lead Configuration	Bipolar	Bipolar	Same LV configuration as the Pacing Test For MRI and MRI +1 Month visits: The same LV Pacing Configuration must be used for impedance testing
Sensing Tests	RA Sensing Test	RV Sensing Test	LV Sensing Test
Sensing Configuration	Bipolar	Bipolar	Per HCP For MRI and MRI+1 Month visits: The same LV Sensing Configuration must be used for sensing testing
Note: Mode, Lower Rate Limit, Amplitude, Paced AV delay and LV Pacing Lead Configuration shall be set per physician or HCP discretion.			

12.5.1.1 Manual Right Atrial Threshold Test

If the subject does not have an active implanted RA lead, then skip to the next section.

Otherwise, perform a manual RA threshold test following these steps, unless the testing is inhibited by a patient condition (example: subject is in atrial fibrillation):

1. In the Atrial Threshold Test screen set the Test Type to Amplitude
2. Mode, Lower Rate Limit, Amplitude and Paced AV delay shall be set per physician or HCP discretion
3. Pulse Width shall be set to 0.5 ms
4. Cycles per Step shall be set to a minimum of 3
5. Start the annotated real-time ECG from the PRM, then start the manual RA threshold test
 - a. A count of 2 non-capture beats at a given voltage level is required to declare loss of capture (LOC)
 - b. If the subject experiences discomfort during the threshold test due to extracardiac stimulation, then stop the test and perform the manual threshold test per physician discretion.
6. When LOC is determined, stop the threshold test. Stop the PRM real-time ECG a minimum of 2 seconds after LOC is determined.
7. Label the PRM ECG with the subject ID#, date, “[Visit name; e.g. Implant, Pre-Discharge, MRI Visit, MRI + 1Month Visit, etc.] Manual RA threshold test”, attempt # (if applicable).
8. The threshold for the manual RA threshold test is defined as one voltage level above the level where the 2 non-captured beats are observed. Record the threshold in the EDC system.
9. If the threshold saved on the PRM does not match the threshold, as defined in step 8, then update the RA Pace Threshold in the programmer.

12.5.1.2 Manual Right Ventricular Threshold Test

Perform a manual RV threshold test following these steps:

1. In the Right Ventricular Threshold Test screen set the Test Type to Amplitude
2. Mode, Lower Rate Limit, Amplitude and Paced AV delay shall be set per physician or HCP discretion
3. Pulse Width shall be set to 0.5 ms
4. Cycles per Step shall be set to a minimum of 3
5. Start the annotated real-time ECG from the PRM, then start the manual RV threshold test

- a. A count of 2 non-capture beats at a given voltage level is required to declare loss of capture (LOC)
 - b. If the subject experiences discomfort during the threshold test due to extracardiac stimulation, then stop the test and perform the manual threshold test per physician discretion.
6. When LOC is determined, stop the threshold test. Stop the PRM real-time ECG a minimum of 2 seconds after the LOC is determined.
 7. Label the PRM ECG with the subject ID#, date, “[Visit name; e.g. Implant, Pre-Discharge, MRI Visit, MRI + 1Month Visit, etc.] Manual RV threshold test”, attempt # (if applicable).
 8. The threshold for the manual RV threshold test is defined as one voltage level above the level where the 2 non-captured beats are observed. Record the threshold in the EDC system.
 9. If the threshold saved on the PRM does not match the threshold, as defined in step 8, then update the RV Pace Threshold in the programmer.

12.5.1.3 Manual Left Ventricular Threshold Test

If the subject does not have an active implanted LV lead, then skip to the next section.

If multiple manual LV threshold tests are performed, then record the manual LV threshold test that matches the final programmed LV lead configuration following these steps:

1. In the Left Ventricular Threshold Test screen set the Test Type to Amplitude
2. Mode, Lower Rate Limit, Amplitude and Paced AV delay shall be set per physician or HCP discretion
3. Set the pulse width at 0.5 ms
4. Cycles per Step shall be set to a minimum of 3
5. Start the annotated real-time ECG from the PRM, then start the manual LV threshold test
 - a. A count of 2 non-capture beats at a given voltage level is required to declare loss of capture (LOC)
 - b. If the subject experiences discomfort during the threshold test due to extracardiac stimulation, then stop the test and perform the manual threshold test per physician discretion.
6. When LOC is determined, stop the threshold test. Stop the PRM real-time ECG a minimum of 2 seconds after the LOC is determined.

7. Label the PRM ECG with the subject ID#, date, “[Visit name; e.g. Implant, Pre-Discharge, MRI Visit, MRI+1month Visit, etc.] Manual LV threshold test”, attempt # (if applicable).
8. The threshold for the manual LV threshold test is defined as one voltage level above the level where the 2 non-captured beats are observed. Record the threshold in the EDC system.
9. If the threshold saved on the PRM does not match the threshold, as defined in step 8, then update the LV Pace Threshold in the programmer.

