12.7.1 Device Evaluation Prior to Commencement of MR Scan

1. All implanted leads will be evaluated through the implanted PG for **THREE separate consecutive sets of measurements** using the test parameters listed in Table 12-3:
 - Manual pacing threshold tests, as defined in sections 12.5.1.1, 12.5.1.2 and 12.5.1.3.
 - Sensing amplitude
 - Impedance
 - Shock impedance (RV lead only)
2. Test for phrenic nerve stimulation (PNS) and measure the PNS threshold if detected in the programmed LV lead configuration
3. Perform an assessment of Beeper function as defined in section 12.7.1.1.
4. Print the 'Quick Notes' Report

Record the measurements in the EDC system.

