12.8.3 Completing the MRI + 1 Month Visit

1. The PG data must be reviewed to document whether any new episodes of polymorphic or monomorphic VT or VF that required ATP or shock therapy are present, following the MRI visit.
 - a. If polymorphic or monomorphic VT or VF episodes are present:
 - i. Print the ‘Arrhythmia Logbook’ and ‘Selected Episodes Report’ (counters and EGMs) using the PRM
 - ii. A copy of the Selected Episode Report(s) with counters and EGMs is expected to be submitted to Boston Scientific **within 5 business days** using the upload tool in the EDC system
 - iii. If a physical copy of the Selected Episode Report(s) is to be submitted (instead of an electronic upload), the copy is expected to be submitted to the ECG Core Lab **within 5 business days**
2. Program the device according to physician discretion, and indicate if any permanent device programming was changed
3. Print the ‘Quick Notes’ Report
4. Perform a Save All:
 - a. Save device data to a USB using the programmer “Save All” feature
 - b. Label the USB with the subject ID#, Date, and “MRI + 1 month”
 - c. Retain the original USB at the center, a copy is expected to be submitted to Boston Scientific **within 5 business days** using the upload tool in the EDC system
 - i. If a physical copy of the USB is to be submitted (instead of an electronic upload) use a PC to make the copy and label it the same way as the

original. **Do not make a copy by using the programmer a second time as this will create a new USB with slightly different information.**

5. Schedule the Annual follow-up visit.

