13.1.4.1 Hypotheses

The following hypotheses will be used to evaluate the Primary LV Effectiveness Endpoint 1:

H_0 : The LV Pacing Threshold Success Rate $\leq 87\%$

H_A: The LV Pacing Threshold Success Rate > 87%.

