13.1.4.3 Statistical Methods

Multiple LV pacing threshold measurements taken at each of the two visits (MRI Visit and the MRI + 1 Month Visit) will be averaged to determine the average LV pacing threshold at each visit for each subject. The change in average pacing thresholds will then be calculated for each subject and compared to 1.0V to determine success or failure, and the percent of subjects meeting the success criteria will be calculated. [REDACTED]

[REDACTED]

Primary LV Effectiveness Endpoint 1 will be analyzed by per-protocol analysis. The per-protocol analysis will only include subjects who received an MR Scan, and will not include subjects that meet any of the following exclusions:

- Has a medically necessary scan between implant and the MRI + 1 Month Visit
- Fails to meet labeled MRI Conditions of Use
- Experiences a lead-related complication between MRI Visit and the MRI + 1 Month Visit
- Has an incomplete scan based on the ENABLE MRI Study MR Scan Sequences

The per-protocol analysis will consider the subjects without paired LV pacing threshold measurements as having missing data, in addition to any subject that meets an exclusion

listed above. To assess the impact missing data could have on the analysis results, a tipping point analysis will be conducted. The analysis will assign each subject with missing data as either a failure or success. All possible combinations of these patients' data will be evaluated along with the actual observed data to find the point, if any, at which the endpoint has failed.

13.1.5 Primary LV Effectiveness Endpoint 2: Pre-MR scan vs. 1 Month Post-MR Scan LV Sensed Amplitude

Decreases in average LV sensed amplitude pre-MR scan and 1 Month post-MR scan will be calculated for subjects. Subjects will be considered a success if the average sensed amplitude at the MRI + 1 Month Visit remains ≥ 5.0 mV and above 50% of the average pre-MR Scan value. Subjects who have an average pre-scan LV sensed amplitude measurement < 5.0 mV will be excluded from this analysis.

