13.4.2 Control of Type I Error

Each primary effectiveness endpoints can be tested at the significance level of 5% and the primary safety endpoint can be tested at the significance level of 2.5% while still maintaining the overall type I error level at no greater than 5%. This follows the methodology of the Intersection-Union Test (IUT).

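### At the MRI and MRI + 1 Month visits, Table 12-3 and section 12.5.1.3 can name different LV threshold values to record for Primary LV Effectiveness Endpoint 1

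*Combined protocol and SAP*

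**What the plan says.** All locations are in the combined protocol and SAP.

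- **Table 12-3 (12.5.1), LV threshold column.** For the MRI and MRI + 1 Month visits: "The same LV Pacing Configuration must be used for threshold testing". The table has parallel rules for LV impedance and LV sensing.
- **Note under Table 12-3.** "LV Pacing Lead Configuration shall be set per physician or HCP discretion". It names no visit and makes no exception.
- **12.5.1.3.** When more than one manual LV test is done, the site is to "record the manual LV threshold test that matches the final programmed LV lead configuration". Step 8 sends the threshold to the EDC. Step 7 lists the MRI Visit and the MRI + 1 Month Visit among its labelling examples, so the section is not confined to implant.
- **12.7.1, 12.7.4 and 12.8.1.** The pre-scan, post-scan and one-month evaluations each call for three sets of measurements "using the test parameters listed in Table 12-3", and each also cites 12.5.1.3 for the manual LV test.
- **12.8.3, after the one-month evaluation.** "Program the device according to physician discretion, and indicate if any permanent device programming was changed". Section 12.7.5 has the same step at the MRI Visit.
- **13.1.4.3.** Measurements are averaged within each visit, and then "The change in average pacing thresholds will then be calculated for each subject and compared to 1.0V to determine success or failure". Subjects without paired LV thresholds count as missing and enter a tipping point analysis. Part of this section is redacted.

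**The concern.** A change from pre-scan to one month describes the scan's effect on the lead only if both values come from the same electrodes. The LV lead is quadripolar and offers a variety of pace/sense configurations (section 5.4), so a change of vector is a real possibility.

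Table 12-3 speaks to which vector is tested. Section 12.5.1.3 speaks to which result is recorded. A site can therefore test the pre-scan vector at one month as Table 12-3 requires, test a second vector, program the second, and follow 12.5.1.3 by recording the second. The endpoint then compares two different vectors. The readable part of 13.1.4.3 does not say that such a pair is unpaired. It could enter as observed data and escape the tipping point analysis.

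At stake is which number enters a primary endpoint for the subjects affected.

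**Working it through.** **Step 1. The instructions side by side at the MRI + 1 Month Visit**

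| Situation at one month | Value under Table 12-3 | Value under 12.5.1.3 | Same? |
|---|---|---|---|
| Only the MRI Visit vector (A) is tested | A | A (multiple-test rule not needed) | Yes |
| A and B tested, A left programmed | A | A | Yes |
| A and B tested, B programmed | A | B | No |

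The conflict is confined to the last row.

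**Step 2. What a mismatched pair does to one subject** (illustrative voltages, success limit 1.0 V)

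- Hidden failure: A is 1.0 V before the scan and 3.0 V at one month, so the change is 3.0 − 1.0 = +2.0 V, a failure. If B at 1.4 V is recorded instead, the change is 1.4 − 1.0 = +0.4 V, a success.
- False failure: A stays at 1.0 V, but the vector is changed for another reason, such as phrenic nerve stimulation, to one that measures 3.0 V. The recorded change is +2.0 V although A did not change.

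**Step 3. Scale, as illustration only**

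The plan has no figure to reproduce: the expected rate, power and LV sample size are redacted or blank. Inputs:

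- goal p0 = 87% (13.1.4.1);
- one-sided exact binomial test (synopsis, Statistical Methods);
- 5% level (13.4.2), taken as one-sided;
- N from 75 to 200 (assumption);
- true success rate 87%, the null boundary (assumption);
- fraction h of true failures recorded as successes, h = 10% (assumption).

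Critical count: the smallest r with P(X ≥ r | N, 0.87) ≤ 0.05.

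Observed success rate under masking: 0.87 + 0.13 × h = 0.87 + 0.013 = 0.883.

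| N (assumed) | r | Failures allowed | P(pass), no masking | P(pass), 10% of failures masked |
|---|---|---|---|---|
| 75 | 71 | 4 | 2.6% | 5.2% |
| 100 | 93 | 7 | 4.3% | 9.0% |
| 120 | 111 | 9 | 4.2% | 9.3% |
| 125 | 116 | 9 | 2.9% | 7.0% |
| 150 | 138 | 12 | 3.8% | 9.5% |
| 200 | 183 | 17 | 3.2% | 9.3% |

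If the mismatches instead added false failures equal to 10% of the true ones, the observed rate would be 0.87 − 0.013 = 0.857. The chance of passing would then be 0.9% to 1.9% over the same N. The effect is not signed by the text alone.

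**Step 4. Can a mismatch be seen afterwards?** Partly. Sites report permanent programming changes and submit a Save All (12.7.5, 12.8.3), and they keep the threshold strips. However, the strip label in 12.5.1.3 step 7 carries subject, date, visit and attempt but not the vector. The source lists in Tables 12-6 and 12-7 do not name the LV configuration tested.

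**The case against.** The strongest reply is that Table 12-3 already covers this case. Its rule is mandatory, is written for exactly the two visits that feed the endpoint, and is invoked by both evaluations. Section 12.5.1.3 is a generic procedure reused from the implant visit. On ordinary reading, a visit-specific requirement controls a general recording instruction and a general discretion note. This largely stands: Table 12-3 is the more natural controlling rule. What remains is that the text does not say so. A site that tests in the same vector and then follows 12.5.1.3 breaks no testing rule.

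The path is also narrow. It needs a second vector tested at one month, that vector programmed, and its values entered. Because three sets are averaged, full substitution needs three sets in the new vector. This stands, and it limits the likely frequency.

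A reader might infer that the error runs one way, always hiding failures. The documents do not support that. Phrenic nerve stimulation is tested at the same evaluations and is another possible reason to change vector, and such a change can produce a false failure. Hiding failures is the more likely direction only when a threshold rise caused the switch.

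A reader might also infer that the pre-scan value is undefined, because final programming follows the scan. That goes too far: 12.7.1 already refers to the programmed LV configuration at the time of the pre-scan evaluation, and Table 12-3 ties the two visits together.

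Finally, 13.1.4.3 is partly redacted, so it cannot be said that the plan lacks a matched-configuration requirement, only that the readable text shows none.

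**Conclusion.** The conflict between instructions is real and bears on a primary endpoint. For a subject tested in two vectors at one month and reprogrammed, Table 12-3 and 12.5.1.3 point to different values. Following 12.5.1.3 would put different vectors into the within-subject change.

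The stronger conclusion, that the plan lets subjects with a raised threshold be scored as successes and so substantially inflates the false-pass rate, is not supported. It would require 12.5.1.3 to override the requirement in Table 12-3 and mismatches to occur often and mostly in one direction. The documents give no frequency. Under the assumptions above, masking 10% of failures lifts the chance of passing at a true 87% from 2.6–4.3% to 5.2–9.5%. Assuming 25% would give 13–33% for N from 75 to 200, but nothing in the documents supports a rate of that size. None of these figures estimates the trial's actual error.

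Severity: moderate. The passages should be reconciled before analysis, but this does not show that the endpoint is invalid as designed.

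**What to change.** 1. **12.5.1.3 and the note under Table 12-3:** state that, for data recording at the MRI Visit and the MRI + 1 Month Visit, the same-configuration rule of Table 12-3 prevails over the final-programmed rule and over the discretion note. Clinical programming is unaffected.
2. **eCRF:** add a field for the LV configuration tested. Enter any other vector's results separately, so that they cannot replace the endpoint value.
3. **13.1.4.3:** unless the redacted text already does so, define paired LV thresholds as measured in the same configuration. Treat mismatched pairs as missing and include them in the tipping point analysis. This inclusion matters because a switch may itself follow a threshold rise, so these subjects may not be missing at random.

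Cost: wording in three places and one or two eCRF fields. No extra test is needed, since Table 12-3 already requires the same-configuration test. The downside is that a few mismatched pairs become missing.
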